7.1. Blood Sample Collection

Blood will be collected from an accessible vein at the protocol-defined time points.

After each collection interval, primary samples will be shipped by overnight carrier to the address below. Duplicate samples will be stored at the clinical site for shipment as and when requested.

[name]
[name]
[name]
UNITED STATES OF AMERICA

[contact] E-mail:

cc: [contact] cc:

Before shipping, the recipient ([contact], [contact], and [contact]), Study Director, Study Coordinator, and Study Monitor will be notified by e-mail as to the date and method of sample shipments.

40

Protocol ST-2427-CS-001/ SiteOne Therapeutics, Inc. 5UG3 DA049599-01 (Amendment 3)

Page 39 of 62

7.2. Urine Sample Collection

Urine samples will be collected at the protocol-defined intervals in the SAD.

During each protocol-defined urine collection interval, urine will be pooled in 0hr - 4hr, 4hr – 8hr, 8hr – 12hr, 12hr – 24hr and 24hr – 48hr collection windows and the collection time and volume for each collection recorded. Pooled urine samples will be maintained refrigerated and processed at the end of each 4-hour pooled collection. Approximately 200 μL of urine from each 4-hour pool will be added to a tube containing approximately 200 μL of ammonium acetate buffer (provided by Alturas Analytics as a 500 mM, pH 5.4 ammonium acetate buffer and stored at ambient conditions) and placed on wet ice or chilled cryoracks for up to 6 hours until stored in a freezer, set to maintain approximately –70°C. This will be repeated 2 more times to create 3 samples of urine/ammonium acetate mixture for every 4-hour pool. Any remaining urine will be discarded.

Samples will be collected, stored, and shipped as described above for the whole blood samples.

7.3. Sample Analysis

Whole blood and urine analysis for ST-2427 will be conducted by Alturas Analytics using validated HPLC-MSMS methods (TM20-573, urine; TM20-574, whole blood:buffer), and in accordance with the guidelines indicated in Alturas Analytics' SOPs.

Incurred sample reproducibility will be conducted in accordance with Test Site standard operating procedures on whole blood and urine samples. Results will be included in the analysis report.

When requested, ST-2427 concentrations in blood and urine will be transferred to the Sponsor-designated PK expert. These data will be analyzed using standard compartmental models (described in Section 9) for determination of PK parameters in time for the DMC meetings at the end of each cohort.

Confidential and Proprietary Page 40 of 62

8. ASSESSMENT OF SAFETY

8.1. Safety Parameters

8.1.1. Demographic/Medical History

Demographics, including sex, age, race, ethnicity, and medical history including body weight, height, BMI, concomitant medications, and child-bearing potential (for women) will be recorded during Screening. These data will be used to evaluate eligibility for the trial. Demographics and medical history will be summarized as Baseline characteristics in the Clinical Study Report.

In addition, exploratory analyses of the effects of Baseline parameters (e.g., sex, body weight) on ST-2427 PK may be undertaken (refer to Section 9.2).

8.1.3. Weight, Height and Body Mass Index

Body weight and height will be measured and recorded for all subjects in the SAD during screening and upon admission for the confinement (on Day -1). BMI will be computed from body weight and height at all observation time points.

8.1.4. Physical Examination

The Investigator will perform a physical examination on all subjects at Screening, upon admission for the confinement, at the Follow-Up visit and for Symptom directed Physical Examination at discharge. Physical examinations will include assessments of possible medical signs or symptoms from clinical observation and subject interview per site SOPs. All findings will be recorded on case report forms.

8.1.5. Local Injection Site Irritation

Consistent with Food and Drug Administration (FDA) guidance, *Guidance for Industry Toxicity Graading Scale for Healthy Adult and Adolescent Volunteers Enrolled in Preventative Vaccine Clinical Trials, (2007)*, the assessment of local irritation at the injection site will be performed at the visits noted in Table 4 and Appendix D. The scale consists of 4 categories with each graded on a scale from 1 to 4 based on clinical abnormality. The scale is provided in Appendix D.

8.1.6. Electrocardiogram (ECG)

At Screening, ECGs will be recorded from all subjects in the SAD to evaluate and confirm subject eligibility for the trial.

Telemetry will be performed for detection of arrhythmias for 12 hours on Day 1 in SAD.

ECGs will be extracted at time points detailed in Schedule of Events.

8.1.7. Laboratory Assessments

Blood samples will be collected at pre-defined time points for evaluation of clinical laboratory tests (Appendix B), and the PK of ST-2427. The total blood volume to be collected from each subject in this study is approximately 65.2 mL during participation in the SAD (Appendix C). All hematology and blood chemistry analyses will be conducted by a central laboratory.

8.1.7.1. Hematology

At Screening, at the protocol-defined time points during the confinement periods for the SAD, and at the Follow-Up visit, blood samples will be collected for analysis of hematology. At each of these time points, approximately 4 mL of venous blood will be collected into potassium EDTA tubes.

8.1.7.2. Blood Chemistry

At Screening, at the protocol-defined time points during the confinement periods for the SAD, and at the Follow-Up visit, blood samples will be collected for analysis of clinical chemistry. At each of these time points, approximately 5 mL of venous blood will be collected in tubes without anticoagulant.

An additional approximately 2.7 mL venous blood sample will be collected into a sodium citrate tube for coagulation tests at Screening.

8.1.7.3. Urinalysis

Urinalyses will be conducted using spot urine sample collections at Screening, Check-In (Day -1), 24 hours, and at the Follow-up visit.

In addition, separate spot urine samples will be collected at Screening for analysis of drugs of abuse (Section 8.1.7.5).

8.1.7.4. Virus Serology

A single, approximately 8.5-mL blood sample will be collected at Screening for testing for human immunodeficiency virus (HIV), hepatitis B surface antigen (HBsAg), or hepatitis C antibodies (HCV). All tests will be conducted by a central laboratory.

8.1.7.5. Drug Screen

At Screening and upon admission for the confinement, a urine alcohol test will be conducted, and a urine sample will be collected for testing for drugs of abuse. Urine drug tests will be conducted by a central laboratory and will screen for amphetamine, methamphetamine, benzodiazepines, barbiturates, cannabinoids, cocaine, cotinine, phencyclidine, methadone, and opioids.

8.1.7.6. Evaluation of Child-Bearing Potential

Women who enroll into this study must be of non-child-bearing potential, e.g., post-menopausal as demonstrated by follicle stimulating hormone, or surgically sterilized by tubal ligation, hysterectomy, bilateral oophorectomy and/or salpingectomy. During Screening, a blood sample will be collected from women and tested for follicle stimulating hormone to confirm eligibility for this

44

Page 43 of 62

study unless documented evidence of surgical sterilization is available and reviewed by qualified study personnel.

8.2. Adverse and Serious Adverse Events

8.2.1. Definition of Adverse Events

8.2.1.1. Adverse Event (AE)

An AE is the development of an undesirable sign (including an abnormal laboratory finding), symptom, medical condition or the deterioration of a pre-existing medical condition following or during exposure to a pharmaceutical product, whether or not considered casually related to the product. In clinical studies, an AE can include an undesirable medical condition occurring at any time, including baseline or washout periods, even if no study treatment has been administered.

It is the responsibility of the investigator to document all AEs that occur during the study. All AEs that occur after any patient/subject has been enrolled, before treatment, during treatment, or at any time up to the Follow-Up visit, whether or not they are related to the study, must be recorded on the appropriate case report forms (CRFs).

8.2.1.2. Serious Adverse Event (SAE)

A SAE is an AE occurring during any study phase (i.e., Baseline, treatment, washout, or Follow-Up), and at any dose of the investigational product, comparator, or placebo, that fulfils one or more of the following:

- Results in death
- It is immediately life-threatening
- It requires in-patient hospitalization or prolongation of existing hospitalization
- It results in persistent or significant disability or incapacity
- Results in a congenital abnormality or birth defect
- It is an important medical event that may jeopardize the patient or may require medical intervention to prevent one of the outcomes listed above.

Page 44 of 62

All SAEs that occur after any patient/subject has been enrolled, before treatment, during treatment, or at any time up to the Follow-Up visit, whether or not they are related to the study, must be recorded on the appropriate CRF.

Definition of Terms

Life-Threatening: An AE is life-threatening if it places the subject at immediate risk of death from the event as it occurred (i.e., it does not include an event that, had it occurred in a more severe form, might have caused death). For example, drug induce hepatitis that resolved without evidence of hepatic failure would not be considered life-threatening, even though drug induced hepatitis can be fatal.

Hospitalization: An AE requiring hospitalization should be considered an SAE. Hospitalization scheduled for an elective procedure or treatment of a pre-existing condition that has not worsened during the participation in the trial (e.g., elective surgery for a pre-existing condition that has not worsened), or for a routine clinical procedure that is not the result of an AE is not considered as an AE, either serious or non-serious, according to the defined criteria.

In general, hospitalization signifies that the subject has been detained (usually involving at least an overnight stay) at the hospital or emergency department for observation and/or treatment that would not have been appropriate in the physician's office or outpatient setting.

Disability/Incapacity: An AE is disabling or incapacitating if the event results in a substantial disruption of a subject's ability to conduct normal life functions.

8.2.1.3. Other Adverse Events

Other AEs will be identified by the Drug Safety Investigator and if applicable also by the Clinical Study Team Investigator during the evaluation of safety data for the Clinical Study Report. Significant AEs of particular clinical importance, other than SAEs and those AEs leading to discontinuation of the patient/subject from the study, will be classified as other AEs. For other AEs, a narrative may be written and included in the Clinical Study Report.

8.3. **Relationship to Study Drug**

An Investigator who is qualified in medicine must make the determination of relationship to the investigational product for each AE (Unrelated, Possibly Related, or Probably Related). The Investigator should decide whether, in his or her medical judgment, there is a reasonable possibility that the event may have been caused by the investigational product. If no valid reason exists for suggesting a relationship, then the AE should be classified as "unrelated." If there is any valid reason, even if undetermined, for suspecting a possible cause-and-effect relationship between the investigational product and the occurrence of the AE, then the AE should be considered "related."

If the relationship between the AE/SAE and the investigational product is determined to be "possible" or "probable" the event will be considered related to the investigational product for the purposes of expedited regulatory reporting.

8.4. **Recording Adverse Events**

AEs spontaneously reported by the patient/subject and/or in response to an open question from the study personnel or revealed by observation will be recorded during the study at the investigational site. Clinically significant changes in laboratory values, blood pressure, and pulse need not be reported as AEs. However, abnormal values that constitute an SAE or lead to discontinuation of administration of study drug must be reported and recorded as an AE. Information about AEs will be collected from the Screening at enrollment until the end of the study. SAE information will be collected from the first administration of study drug until the Follow-up visit. The AE term should be reported in standard medical terminology when possible. For each AE, the investigator will evaluate and report the onset (date and time), resolution (date and time), intensity, causality, action taken, serious outcome (if applicable), and whether or not it caused the patient to discontinue the study.

Intensity will be assessed according to the following scale:

- Grade 1: Mild (awareness of sign or symptom, but easily tolerated)
- Grade 2: Moderate (discomfort sufficient to cause interference with normal activities)
- Grade 3: Severe (incapacitating, with inability to perform normal activities)
- Grade 4: Potentially Life Threatening (emergency room visit or hospitalization)

Should a pregnancy occur, it must be reported and recorded on the pregnancy reporting form. Pregnancy in itself is not regarded as an AE unless there is a suspicion that an investigational product may have interfered with the effectiveness of a contraceptive medication.

The outcome of all pregnancies (spontaneous miscarriage, elective termination, normal birth, or congenital abnormality) must be followed up and documented even if the patient was discontinued from the study.

Page 45 of 62

Page 46 of 62

All reports of congenital abnormalities/birth defects are SAEs. Spontaneous miscarriages should also be reported and handled as SAEs. Elective abortions without complications should not be handled as AEs.

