Orthostatic tests will be performed pre-dose (within 60 minutes prior to study drug administration), and at 0.5, 1, 1.5, 2, and 2.5 hours (± 10 minutes) after start of infusion. For these tests, subjects should be standing for 3 minutes with measurements of heart rate and blood pressure (SBP, DBP) at 1, 2, and 3 minutes after standing

- d e
- f COVID-19 test will be performed after Screening is complete and subject is confirmed, but prior to check-in to the unit
- g A blood sample will be collected from women and tested for follicle stimulating hormone to confirm eligibility for this study unless documented evidence of surgical sterilization is available and reviewed by qualified study personnel.
- h Subjects will be confined at the clinic from the day before study drug infusion through at least 48 hours after the start of study drug infusion. This is predicted to exceed the time necessary for the concentration of ST-2427 to decrease to <5% of the peak concentration. During the study, the period of confinement may be extended if the drug elimination is found to be slower than predicted in the first cohort(s). Subjects will be discharged only if clinically significant AEs, if any, are resolved.
- i Study drug is to be administered intravenously as a 1-hour infusion. A ±10-minute window is allowed for the duration of infusion, and a ±15-minute window is allowed for the start of infusion relative to the nominal time.
- j Whole blood samples collected for PK analysis should be collected at the specified time. When blood sample collections coincide with other assessments, assessments should be conducted in the following orders for PK will be collected at the following time points:
 - Day 1: pre-dose, and 0.25, 0.5, 0.75, 1, 1.15, 1.3, 1.5, 2, 2.5, 3, 4, 6, 8, 10, 12, 24, 48
 - Predose PK samples should be collected within approximately 60 minutes prior to dosing

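### Section 8.4 exempts clinically significant laboratory changes from AE reporting, against the AE definition in Section 8.2.1.1, so non-serious findings can drop out of the AE summaries without grade or causality

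*Combined protocol and SAP*

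**What the plan says.** Section 8.2.1.1 defines the term broadly: "An AE is the development of an undesirable sign (including an abnormal laboratory finding), symptom, medical condition". It then sets the duty: "It is the responsibility of the investigator to document all AEs that occur during the study". The same section makes CRF entry mandatory whether or not the event is related to the study.

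Section 8.4 carves out an exemption: "Clinically significant changes in laboratory values, blood pressure, and pulse need not be reported as AEs". It limits that exemption in the next sentence: "abnormal values that constitute an SAE or lead to discontinuation of administration of study drug must be reported and recorded as an AE".

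What an AE entry brings with it is also set in Section 8.4: "For each AE, the investigator will evaluate and report the onset (date and time), resolution (date and time), intensity, causality, action taken". Section 8.3 asks for a relationship judgement for each AE. The Synopsis and Section 9.1 apply the FDA 2007 toxicity grading to AEs, and Section 9.1 summarises subjects with AEs by system organ class and preferred term. Outside the AE tables, Section 9.1 plans descriptive statistics for laboratory data and change from baseline for blood pressure and heart rate.

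**The concern.** A site cannot treat Section 8.2.1.1 as mandatory and also use the exemption in Section 8.4. The exemption is not confined to trivial deviations: it names the changes judged clinically significant, which are the ones an AE listing most needs.

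This is a first-in-human study, and its primary objective is safety and tolerability. A laboratory change that is not entered as an AE has no coded term, is not counted by system organ class or preferred term, gets no investigator causality judgement, and falls outside the planned toxicity grading. The AE summary would then rest on whichever of two incompatible instructions the site happened to follow.

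**Working it through.** The check is mainly a comparison of text. One piece of arithmetic shows how far the exceptions in Section 8.4 reach.

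**1. Is there a conflict?** Take a non-serious, clinically significant laboratory abnormality first seen after dosing.

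| Question | Section 8.2.1.1 | Section 8.4 |
|---|---|---|
| Is it an AE? | Yes, laboratory findings are named | Need not be reported as one |
| Must it go on the CRF as an AE? | Yes, as for all AEs | Only if an SAE or if it stops study drug administration |

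The answers differ. Separating reporting from recording does not rescue Section 8.4, because its exception sentence uses both verbs together.

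**2. Does the conflict cover blood pressure and pulse?** Section 8.2.1.1 does not name them. They come in only as undesirable signs. The published text lacks Section 8.1.2, Table 4 footnotes d and e, and the stopping criteria of Section 3.4.1, any of which might bear on this. For these measures the conflict is therefore an inference.

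**3. Do the exceptions close the gap for scheduled laboratory tests?** Inputs, in minutes from the start of infusion (time zero in Table 4 footnote a):

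- Planned infusion: 60 min, with a duration window of ±10 min (Table 4 footnote i). Latest allowed end: 60 + 10 = 70 min. The separate ±15 min window for the start does not matter, because time runs from the actual start.
- Earliest scheduled post-dose chemistry, haematology and urinalysis: nominal 24 h (Table 4; Section 8.1.7.3 for urinalysis), that is 24 × 60 = 1440 min.
- Gap: 1440 − 70 = 1370 min = 22 h 50 min.

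No scheduled post-dose laboratory result can lead to discontinuation of an infusion that is already over. For those tests only the SAE exception is left. It does include the important-medical-event criterion in Section 8.2.1.2 ("It is an important medical event that may jeopardize the patient or may require medical intervention to prevent one of the outcomes listed above"), but a change that is clinically significant and not serious remains exempt.

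The point is limited to scheduled tests. Appendix C allows extra safety samples, and one drawn during the infusion could still lead to discontinuation. Nor does it carry over to orthostatic blood pressure and heart rate, which are measured at 0.5 and 1 h.

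**4. How many findings are affected?** This cannot be derived from the documents. I also give no count of tests, because Table 4 marks five chemistry and five haematology times while Appendix C lists four samples of each. The timing result does not depend on which is right. For scale only: with 4 active subjects per cohort, one omitted finding shows as 0/4 instead of 1/4 in that cohort.

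**The case against.** The strongest reply is that Section 8.2.1.1 is a general definition and Section 8.4 a specific, permissive recording rule that leaves values in the laboratory and vital-sign datasets. On that reading the defect is a missing cross-reference. It is a possible reading, but it has to override a mandatory instruction to record all AEs, and nothing visible says that Section 8.4 prevails. The wording may be a slip. If so, it still needs correcting.

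Several mitigations are real:

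- Laboratory values and blood pressure and heart rate changes are still summarised under Section 9.1.
- The DMC looks at the clinical and PK data as a whole before each next cohort (Section 9.7), not only at AE tables.
- Section 8.4 also has AEs recorded when volunteered, elicited or observed, so a symptom accompanying an abnormal value is still captured. The gap is mainly isolated, asymptomatic, non-serious values.
- ECG findings are not on the exempt list, and Section 9.3 plans an outlier analysis for them.
- There is a single site, which narrows inconsistency between subjects.

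None of these supplies an AE term, a causality judgement or a count for the exempt laboratory finding, and no laboratory outlier analysis is visible. Section 8.2.1.3 adds a search for other significant AEs "during the evaluation of safety data for the Clinical Study Report", but does not say whether it reaches changes never entered as AEs.

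The objection also says that the 22 h 50 min figure measures no effect on a safety summary. That is correct. It shows only that one of the two exceptions is empty for scheduled laboratory tests.

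**Conclusion.** The concern holds. For laboratory findings the two sections give incompatible instructions, and confidence is high. For blood pressure and pulse confidence is moderate, because the conflict is inferred and relevant text is not visible.

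What is lost is the AE record of non-serious, clinically significant laboratory changes: term, grade, causality and incidence count. The measurements themselves are kept. The size of the loss cannot be estimated, no percentage effect is claimed, and nothing here implies bias between the arms. The timing result assumes that samples are taken at the nominal 24 h and that the infusion stays within its allowed window.

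This should be fixed. It does not invalidate the planned analyses, but it weakens the AE summary that serves the primary objective, and the correction is cheap.

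**What to change.** Remove the exemption for clinically significant changes from Section 8.4, and state one common recording threshold there and in Section 8.2.1.1. Both sections need the edit: Section 8.2.1.1 attaches no clinical-significance condition to a laboratory finding, so changing Section 8.4 alone would leave a mismatch. Findings below the threshold stay in the laboratory and vital-sign data only.

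Reconcile Table 4 footnote h in the same amendment. It says "Subjects will be discharged only if clinically significant AEs, if any, are resolved", so recording more changes as AEs could affect confinement. How that is resolved is for the sponsor.

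The cost is two text edits, the reconciliation of footnote h, updated CRF completion guidance and a few more AE records. No extra subjects are needed.
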